7.4.5.4 Pupillary diameter

It is the opening in the middle of the iris through which light enters the eyeball. Its diameter is determined by the balance between the pupillary sphincter muscle and the radial fibers of the iris (pupil dilator). Normal values are 2–6 mm. [33]

Since the research product is not a mydriatic, we will consider significant changes in the pupil of the research subjects of > 2 mm (pharmacological mydriasis), whether this change is in photopic or mesopic vision. The measurement will be performed using any of the following tools: OPD III, autorefractors, or topographers that include these measurements. We will only require that the tool used be the same for all patients at the research center and for all their visits. The measurement must always be performed in the same office, under the same artificial lighting conditions, and that the patient be in the room for at least 5 minutes before the measurement.

If there is a change greater than 2 mm between the baseline visit and any of the other measurements, the product will be considered to have produced pharmacological mydriasis, also if there is this change between the examination before and after the application of the investigational product at visits 1 and 2. This change will also be considered an adverse event.

7.4.5.5 Conjunctival hyperemia

It is defined as the simplest reaction of the conjunctiva to a stimulus. A red appearance is observed secondary to vasodilation of the conjunctival vessels of varying intensity. It is graded using the Efron scale. [38]

Figure 1. Efron scale for conjunctival hyperemia

Management as AE: Grade 3 and 4 at visits 1, 2 and final will be considered as aggravation and adverse event.

7.4.5.6 Best-corrected visual acuity

Visual acuity (VA) is a test of visual function. Spatial visual acuity is the ability to distinguish separate elements of an object and identify them as a whole. It is quantified as the minimum angle of

separation (located at the nodal point of the eye) between two objects that allows them to be perceived as separate objects.

Snellen notation is described as the distance at which the test is performed divided by the distance at which the letter is vertically equivalent to 5 minutes of arc. Thus, at 6 meters a letter 6/6 (20/20) is equivalent to 5 minutes of arc, a letter 6/12 (20/40) is equivalent to 10 minutes, and a letter 6/60 (20/200) is equivalent to 50 minutes. The Snellen fraction can also be expressed as a decimal (i.e. 20/20 = 1 and 20/40 = 0.5).[34]

VA will be assessed at baseline, without refractive correction, using the Snellen chart. This chart will be placed in a location with adequate natural or artificial lighting and at a distance of 3 m from the subject being assessed. Visual acuity will be measured in the study eye, asking the subject to keep both eyes open and using an occluder to cover the contralateral eye. The subject will read aloud the lines indicated by the evaluator. The line with the smallest letters visible will be recorded by the evaluator as a fraction of the OD VA in the clinical record.

The subject's best refractive correction will then be performed, and the examination will be repeated using the obtained refraction. This result will be reported as best-corrected visual acuity, recorded as a fraction and decimal in both the clinical record and the eCRF .

Management as AE: A decrease of 2 or more lines of vision in BCVA compared to that obtained at the baseline visit will be considered an adverse event.

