5.1 Eligibility criteria

5.1.1 Inclusion criteria

- Be clinically healthy
- Have the ability to voluntarily grant signed informed consent
- Be able and willing to comply with scheduled visits, treatment plan, and other study procedures
- Be between 18 and 45 years old.
- Women of childbearing potential must ensure continued use (started \geq 30 days prior to signing the ICF) of a hormonal contraceptive method or intrauterine device (IUD) during the study period.
- Have a best-corrected visual acuity of 20/30 or better in both eyes.
- Have vital signs within normal parameters.
- Have an intraocular pressure \geq 10 and \leq 21 mmHg.

5.1.2 Exclusion criteria:

- Be a user of topical ophthalmic products of any kind.
- Being allergic to naphazoline or having a history of intolerance to nasal decongestants or ocular vasoconstrictors.
- Have a history of a suspected diagnosis of primary angle closure, primary angle closure, or angle-closure glaucoma.
- Having iridotomies or waiting for iridotomies.
- Have conjunctival hyperemia grade 3 and 4 on the Efron scale.
- Have ocular surface staining with a value equal to or greater than 3 on the SICCA scale in either eye.
- Being a user of medications or herbal products, by any other route of administration.
- For women: be pregnant, breastfeeding, or planning to become pregnant during the study period.
- Having participated in clinical research studies 90 days prior to inclusion in this study.
- Having previously participated in this same study.
- Be a contact lens user who cannot discontinue use during the study.
- Having a history of any chronic-degenerative disease, including diabetes and high blood pressure.
- Present inflammatory or infectious disease, active at the time of entering the study.
- Present unresolved injuries or traumas at the time of entering the study.
- Have a history of any type of eye surgery
- Having undergone non-ophthalmological surgical procedures in the last 3 months.

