6.1.2 Dose of the investigational product

- Dosage: 1 drop 4 times a day in both eyes (AO).

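### The acuity procedure is written for one undefined study eye although both eyes are treated, so a left-eye BCVA loss at visits 1, 2 and final can go unrecorded

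*Protocol*

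**What the plan says.** Protocol 7.4.5.6 describes how acuity is taken; section 7.5.8.1 only refers back to it. The first step is acuity without correction: "Visual acuity will be measured in the study eye, asking the subject to keep both eyes open", with an occluder over the other eye. The smallest line read is "recorded by the evaluator as a fraction of the OD VA in the clinical record". Refraction follows, and "the examination will be repeated using the obtained refraction"; that result is the BCVA, entered in the clinical record and the eCRF, with no eye named. The AE rule for this variable is "A decrease of 2 or more lines of vision in BCVA compared to that obtained at the baseline visit", again with no eye named.

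Elsewhere the plan is for two eyes. Protocol 6.1.2 and 7.5.11 and SAP 3.4 give the product in both eyes. Protocol 5.1.1 requires: "Have a best-corrected visual acuity of 20/30 or better in both eyes". Protocol 10.1 and SAP section 4 have 22 subjects contributing both eyes. Section 7.4.5.7, directly after the acuity section, has staining grades entered for OD and OS.

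**The concern.** A study eye belongs to a design in which one eye is treated or one eye is chosen for analysis. This trial does neither, and no section of the protocol or SAP says how such an eye would be picked. The only hint is the OD label, which points to the right eye.

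BCVA is a secondary outcome (Protocol 7.4.2), and a fall of two or more lines is a defined AE. The protocol also gives a reason to look for such a fall: section 2.5.1 mentions drug-induced mydriasis with reduced vision, and 7.4.5.9 lists blurred vision among the possible events. In a safety and tolerability study, a procedure that can be followed correctly while leaving one treated eye untested weakens a prespecified safety measure. The analysis cannot repair this. Protocol 10.4 plans no imputation, and 10.3.2.2 analyses secondary variables only as far as the measurements exist.

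**Working it through.** The plan states no figure to reproduce on this point, so the main check is a comparison of texts.

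1. **Procedure.** One eye is examined at a time with the other covered. The text names a single eye and has no step for repeating the test on the fellow eye.
2. **Uncorrected acuity.** Recorded for OD only.
3. **BCVA.** It is the same examination repeated with the refraction, so it inherits the one-eye procedure. It does not inherit the OD label, because its own recording sentence names no eye.
4. **AE rule.** It compares BCVA with the baseline visit and does not say whether either eye can trigger it.
5. **Entry.** The 20/30 criterion covers both eyes, 7.5.3 requires every criterion to be checked, and 7.7.1 lists BCVA at baseline. A left-eye BCVA must therefore exist at entry.
6. **Later visits.** The schedule (Protocol 1.3 and Table v), the visit lists (7.7.2 to 7.7.4), Table iii, and SAP Tables 1 and 2 all list BCVA without naming an eye. Nothing in them makes up for the one-eye wording in 7.4.5.6.

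The gap is therefore left-eye BCVA at visits 1, 2 and final.

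**Count of eyes.** Protocol 10.1 gives 22 subjects contributing OA, which I read as both eyes (the SAP abbreviation list has AO). 22 × 2 = 44 treated eyes. Under the literal reading one eye per subject is followed, so 44 − 22 = 22 treated eyes have no BCVA after entry.

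**Illustration of what could be missed.** The documents give no risk of a two-line loss, so I assume a per-eye risk q of 2%, 5% or 10%, with eyes independent.

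- Risk that a subject is affected in at least one eye: P = 1 − (1 − q)²
- Share of affected subjects missed if only OD is measured: 1 − q/P
- Chance of recording at least one case in 22 subjects: 1 − (1 − P)²² with both eyes measured, 1 − (1 − q)²² with OD only

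| q | P | Share missed | At least one case, both eyes | At least one case, OD only |
|---|---|---|---|---|
| 2% | 0.0396 | 49.5% | 0.589 | 0.359 |
| 5% | 0.0975 | 48.7% | 0.895 | 0.676 |
| 10% | 0.19 | 47.4% | 0.990 | 0.902 |

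For q = 2%: P = 1 − 0.98² = 0.0396 and 1 − 0.02/0.0396 = 0.495. If losses in the two eyes of a subject are positively correlated, the share missed is smaller. The table also assumes that no other examination detects the loss, so it is an upper illustration and not a forecast.

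**The case against.** The strongest reply is that this is loose wording which any ophthalmology site would read sensibly. The sentence describes ordinary monocular testing, and the study eye may simply mean the eye being tested. The OD label closes the paragraph on uncorrected acuity, which is not an outcome, an entry criterion or an AE trigger. The English is visibly a translation, so a slip cannot be excluded. Protocol 7.4.5.9 also requires AE questioning and a full ophthalmological evaluation at every visit, and 8.5.1 has the AE record specify the eye where applicable.

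Most of this stands, and it limits the point. Many sites will test both eyes, and a left-eye loss has other routes to detection. Those routes do not replace a line count against baseline, however: under 7.4.5.9 only findings that the investigator judges to be AEs reach the eCRF. The text still permits one-eye follow-up, and no other section corrects it.

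Three stronger readings are tempting, and the documents do not support them.

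- A reader might infer that the 20/30 criterion cannot be verified in the left eye. It can: the criterion itself compels that measurement at entry.
- A reader might infer that half the treated eyes will have no acuity data and that left-eye losses will be missed. That is only the most literal reading, and it ignores the evaluations just described.
- A reader might infer that testing "at a distance of 3 m from the subject being assessed", when the notation is illustrated at 6 m, relaxes the eligibility limit. The 6 m figures are examples of notation. The section defines the top of the Snellen fraction as the actual test distance, so a subject whose best line at 3 m is the 9 m letter is recorded as 3/9 = 0.33, that is 20/60, and fails 20/30. A relaxed limit would need a 6 m chart and a recorder who ignores that definition, and neither is in the documents.

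**Conclusion.** The point holds as an internal inconsistency that should be corrected. The one-eye acuity procedure in 7.4.5.6 does not fit a trial that doses, qualifies and counts both eyes. Read literally, it yields no left-eye BCVA at visits 1, 2 and final, for up to 22 of 44 treated eyes. A left-eye loss of two or more lines can then go unrecorded unless AE questioning or the general eye examination finds it.

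The count of 22 assumes full planned enrolment and a site that follows the wording exactly, taking OD as the study eye. If the site examines both eyes at each visit, nothing is lost. No primary outcome, sample size or error rate changes. What is at stake is the completeness of one secondary safety outcome and of the AE rule that depends on it.

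**What to change.** In Protocol 7.4.5.6:

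- Replace the reference to the study eye with 'each eye separately'.
- Record uncorrected acuity and BCVA for OD and OS in the source document and the eCRF at every scheduled BCVA assessment.
- Reconcile the AE sentence with the two-eye design, so that it is clear that each eye is compared with its own baseline. The threshold is not in question here.

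The cost is a wording change plus a left-eye eCRF field per assessment if the form lacks one. Visits and sample size stay as they are, and the examination is already needed in both eyes for eligibility. The added work is a few minutes of testing per visit at any site that would otherwise have tested only one eye.

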7.4.5.7 SICCA ocular surface staining

The sequence of ocular surface staining is important for reproducibility and accuracy. Fluorescein should be applied before lissamine green.

Fluorescein staining (TF): A drop of topical anesthetic is instilled in the conjunctival fornix. A second drop is then applied to the tip of the fluorescein strip, allowing it to sit on the strip for 5 seconds to elute the dye, shaking off the excess at the end. A small contact of the strip with the conjunctiva is made in the temporal fornix while the patient looks upward, avoiding damaging the conjunctiva. Corneal fluorescein staining is assessed using a slit lamp with a cobalt blue filter. It is graded according to the Sjögren's Clinical Collaboration Alliance (SICCA) Ocular Staining Grading (OSG). [39]

According to the CTO, grade 0 corresponds to the absence of punctate epithelial erosions (PEEs); grade 1 is defined as the presence of 1-5 PEEs; grade 2 corresponds to 6-30 PEEs; and >30 PEEs will be classified as grade 3. An additional grading point will be added if: 1) PEEs with a diameter of 4 mm are present in the central portion of the cornea; 2) filaments are observed; and 3) confluent staining patches, including linear staining, are observed. [39] See Figure 2.

the grades awarded for corneal staining for OD and OS, respectively, in the file and on the eCFR . The maximum grade per eye is 6.

Lissamine green staining (LGS): After the fluorescein examination, a drop of saline solution is applied to the tip of the lissamine green strip, allowing it to sit on the strip for 5 seconds to elute the dye. A

drop is instilled from the strip into the temporal fornix while the patient looks up, avoiding damaging the conjunctiva. The patient may be asked to blink repeatedly to avoid accumulation in the conjunctival folds. The examination should be performed between 1 and 4 minutes after instillation through a neutral density filter or a red-free filter. It will be graded according to the SICCA CTO. [39]

In CTO, grade 0 is defined as the presence of 0 to 9 lissamine green staining points in the interpalpebral bulbar conjunctiva (with the temporal and nasal portions scored separately); grade 1 is defined as the presence of 10 to 32 points; grade 2 by 33 to 100; and grade 3 by >100 points. Because of the difficulty in counting individual points in a moving eye, any area $\geq 4 \text{ mm}^2$ of confluent points is considered >100 points [39]. See Figure 2.

The PI will record, in the file and in the eCFR, the sum of the grades awarded to the temporal and nasal portions for OD and OS, respectively. The maximum grade per eye is 6.

[figure not shown]

Figure 2SICCA ocular staining grading (Modified from Whitcher et al, 2010)[34]

Ocular surface staining using SICCA is determined by the sum of corneal fluorescein staining and conjunctival lissamine green staining. This is shown in Figure 2. The values that can be obtained for

each eye range from 0 to 12, with staining considered abnormal when a value of 3 or higher is reached.

Management as AE: It will be considered an adverse event when the rating is greater than or equal to 3 points.

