2.3.3 Clinical study of an ophthalmic solution of naphazoline 0.1% and hypromellose 0.5%

An open-label, single-center, observational, prospective clinical study included thirty healthy volunteers. Volunteers were administered a 0.1% naphazoline and 0.5% hypromellose solution four times daily for ten days. Results showed no changes in conjunctival hyperemia, conjunctival discharge, ciliary injection, chemosis, and rose bengal and fluorescein staining. However, 86% of patients experienced burning, 70% of which was mild and the remainder moderate; 6.6% had mild red eyes; and 6.6% had mild ocular pain. The mean burning score was 0.6861, with a standard deviation of 0.42 and a standard error of 0.016. Student's t-test showed a $p > 0.05$, leading to the conclusion that the burning score was not statistically significant. The study concludes that the solution of naphazoline 0.1% and hypromellose 0.5% is safe for application to the ocular surface of healthy volunteers. [28]

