2.7 Justification of the study

Laboratorios Sophia, SA de CV, has conducted a preclinical and phase I clinical study of a similar formulation, but with a higher concentration of components. The reduction in the concentration of the main components (naphazoline and hypromellose) in the PRO-185 solution compared to this formulation studied could mean greater safety of PRO-185, but not necessarily greater tolerance, since the excipients may be involved in clinical manifestations unrelated to the main components.

Menthol has been used in ophthalmic preparations to relieve visual fatigue and ocular discomfort. [23] The inclusion of menthol among the excipients in PRO-185, as well as the lack of clinical evaluation of this formulation, necessitates clinical evaluation of the product. This would provide a more complete safety and tolerability profile.

In a preclinical safety and toxicity study of PRO-185 ophthalmic solution in New Zealand albino rabbits, the drug was shown to be non-toxic and safe to administer. Information also indicates that, at the menthol concentration used in Draize tests, there were no irritating or toxic effects.

Because there is preclinical evidence of safety and toxicity with the PRO-185 formulation, as well as the absence of irritation at the concentration used; and because there are ophthalmic products with menthol as an excipient in similar combinations on other markets, it was decided to advance to clinical research to test the safety and tolerability of PRO-185 in a controlled environment with healthy subjects.

3. Objectives and hypotheses

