6.3 Concomitant treatments and medications (permitted and prohibited)

Any medication used, in addition to appearing in the clinical note, must be recorded in the concomitant medications section of the eCRF .

Permitted medications:

- Ophthalmic:

All permitted medications administered ophthalmically during the study must wait a minimum of 10 minutes after the last application of the study or reference treatments. This is to avoid treatment interactions with the tear film, based on the physiological tear flow rate and volume. [24]

- Tetracaine 0.5%
- Tropicamide 0.8% / Phenylephrine 5%
- Hypromellose 2%
- Fluorescein
- Lissamine green

- Systemic or other routes of administration other than ophthalmic:

- Any hormonal contraceptive will be included, including tablets, injections, and drug-releasing devices.

Prohibited medications:

- Any medication with ophthalmic application that is not on the list of permitted medications
- Any systemic medication that is not on the list of permitted medications.

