7.4.5 Description of the variables, methods and scales for their measurement

7.4.5.1 Intraocular pressure

Tonometry is the objective measure of IOP, based primarily on the force required to flatten the cornea, or the degree of corneal depression produced by a fixed force. Goldman tonometry is based on the Imbert-Fick principle. [34]

Tonometry will be performed after instillation of topical anesthetic with fluorescein and the use of a cobalt blue filter (after assessing surface staining). Two readings will be taken, and the average will be recorded in the clinical record. The average will be recorded in the eCRF .

Management as AEs: IOP peaks ≥ 24 mmHg should be reported as AEs, as well as increases in intraocular pressure greater than 5 mmHg between evaluations before and after application of the investigational product (visits 1 and 2).

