7.5.9 Applying medication during visits

During patient visits, various medications or medical devices may be applied to the ocular surface for ophthalmological examination.

Examples:

- Tetracaine 0.5% ophthalmic solution, used to anesthetize the patient and facilitate measurement of intraocular pressure, application of dyes for staining, and placement of the gonioscopy lens.
- Ophthalmic solution of 0.8% tropicamide and 5% phenylephrine, used to dilate the pupil and better assess the posterior segment.
- PRO-185 ophthalmic solution, an investigational drug, applied at visits 1 and 2.
- Hypromellose 2% ophthalmic solution may be used by the Researcher for gonioscopy assessment.

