7.5.10 Delivery of material for the subject

This refers to the provision of the subject's ID card and the subject's diary. The ID card will serve as identification with the treatment assignment number; this card can also serve as an appointment card. The Subject's Diary is used to record the number of times the treatment is administered.

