7.7.1 Baseline visit

- Consent signature informed
- General and ophthalmological clinical history taking
- Measurement of vital signs (temperature, blood pressure, heart rate, respiratory rate)
- Drug evaluation concomitants
- Measurement of best-corrected visual acuity
- Ophthalmological evaluation (before and after pupil dilation)
- Evaluation of pupil diameter
- Ocular staining with fluorescein and lissamine green
- Measurement of intraocular pressure
- Gonioscopy
- Review of eligibility criteria
- Event evaluation adverse
- Pupil dilation
- Delivery of the investigational product

7.7.2 Visit 1

- Pre-application procedures for the investigational product
 - o Measurement of vital signs (temperature, blood pressure, heart rate, respiratory rate)
 - o Drug evaluation concomitants
 - o Measurement of best-corrected visual acuity
 - o Assessment ophthalmological
 - o Evaluation of pupil diameter
 - o Ocular staining with fluorescein and lissamine green
 - o Measurement of intraocular pressure
 - o Review of continuation criteria
 - o Event evaluation adverse
- Post-application procedures for the investigational product
 - o Measurement of vital signs (blood pressure and heart rate)
 - o Measurement of best-corrected visual acuity
 - o Assessment ophthalmological
 - o Evaluation of pupil diameter
 - o Ocular staining with fluorescein and lissamine green
 - o Measurement of intraocular pressure
 - o Review of continuation criteria
 - o Event evaluation adverse

7.7.3 Visit 2

- Pre-application procedures for the investigational product
 - o Measurement of vital signs (temperature, blood pressure, heart rate, respiratory rate)
 - o Drug evaluation concomitants
 - o Measurement of best-corrected visual acuity
 - o Assessment ophthalmological
 - o Evaluation of pupil diameter
 - o Ocular staining with fluorescein and lissamine green
 - o Measurement of intraocular pressure
 - o Review of continuation criteria
 - o Event evaluation adverse
- Post-application procedures for the investigational product
 - o Measurement of vital signs (blood pressure and heart rate)
 - o Measurement of best-corrected visual acuity
 - o Assessment ophthalmological
 - o Evaluation of pupil diameter
 - o Ocular staining with fluorescein and lissamine green
 - o Measurement of intraocular pressure
 - o Review of continuation criteria
 - o Event evaluation adverse
 - o Return of the research product

- Return of the subject's diary

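### Topical anaesthetic precedes PRO-185 at visits 1 and 2 with no stated interval, so burning and stinging can be masked at the scheduled in-visit doses, and no symptom record is described for the home doses

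*Protocol*

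**What the plan says.** Sections 7.7.2 and 7.7.3 of the protocol each open with a block titled "Pre-application procedures for the investigational product". In both, that block contains fluorescein and lissamine green staining and intraocular pressure. The schedules in 1.3 and 7.6.2 agree: both checks are marked Pre-Tx and again Post-Tx.

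Both checks involve anaesthetic. For staining, "A drop of topical anesthetic is instilled in the conjunctival fornix" (7.4.5.7). For pressure, "Tonometry will be performed after instillation of topical anesthetic with fluorescein" (7.4.5.1). Section 7.5.9 names the agent and its purpose: "Tetracaine 0.5% ophthalmic solution, used to anesthetize the patient and facilitate measurement of intraocular pressure, application of dyes for staining".

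The investigator then applies PRO-185 at the same visit (6.1.3, 7.5.9), and the Post-Tx checks, including adverse events, follow at 20-40 minutes. The one spacing rule, in 6.3, says that permitted ophthalmic drugs "must wait a minimum of 10 minutes after the last application of the study or reference treatments".

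For doses taken away from the clinic, 7.5.10 states: "The Subject's Diary is used to record the number of times the treatment is administered". Section 7.5.13 describes the same use of the diary, for adherence.

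**The concern.** Tolerability is in the trial's title and main objective, and one specific objective (3.1.2) is the incidence of expected and unexpected adverse events. Section 7.4.5.9 lists ocular burning first among the expected events and also names stinging and irritation. Section 2.7 argues that lower concentrations need not mean better tolerance, "since the excipients may be involved in clinical manifestations unrelated to the main components", and gives the inclusion of menthol as a reason for the study. In the sponsor's earlier volunteer study of a stronger product, "86% of patients experienced burning" (2.3.3). Discomfort on instillation is thus the most foreseeable complaint.

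An anaesthetic given shortly before the study drop can suppress exactly that complaint. If few subjects report burning at the observed doses, the data as planned could not separate a well-tolerated product from an anaesthetised surface. For the home doses they could not separate it from incomplete recall.

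**Working it through.** The plan gives no figure to reproduce; the check is one of sequence, followed by two small counts.

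**1. Is the order fixed?** Sections 7.5 and 7.7 let the site rearrange procedures. That freedom cannot move a Pre-Tx check after dosing, because the schedule footnote defines Pre-Tx as before application of the product. Section 7.4.5.9 lets the investigator choose the tonometry instrument, but the anaesthetic drop for staining in 7.4.5.7 remains. So at each of these visits at least one anaesthetic drop precedes PRO-185.

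**2. Does any rule separate the two drops?** Section 6.3 runs one way, from study product to other drops. Its stated reason, interaction in the tear film, is not specific to a direction, but the reverse order has no interval. Section 6.1.3 asks that the visit be completed before 11 a.m. without giving a start time, so it neither forces nor rules out a wait.

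**3. How many applications are involved, per eye?**
- Day 1: 1 to 4 (section 6.1.3 does not fix the number).
- Days 2 to 7: 6 × 4 = 24, of which one is the visit 1 drop.
- Day 8: 1, the visit 2 drop.
- Total: 1 + 24 + 1 = 26 to 4 + 24 + 1 = 29.
- Scheduled in-visit doses in the protocol: 2, that is 2/29 = 6.9% to 2/26 = 7.7% of applications.
- Other applications: 26 − 2 = 24 to 29 − 2 = 27.

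The baseline visit is unsettled. Section 6.1.3 has product administered at its conclusion, SAP Table 1 (section 3.4) marks an in-visit application there, and the protocol schedules mark only visits 1 and 2. A dose given in clinic at the end of baseline would also follow staining and tonometry.

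**4. What could masking do at one in-visit dose?** Expected reports = 22 × r × (1 − m), and P(at least one) = 1 − [1 − r(1 − m)]^22. Here r is the true rate of burning at that dose and m the share masked. Both are assumptions; the 86% row borrows the rate of the earlier, stronger product only as a high value.

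| r | m = 0 | m = 50% | m = 90% |
|---|---|---|---|
| 5% | 1.1 (0.68) | 0.55 (0.43) | 0.11 (0.10) |
| 20% | 4.4 (0.99) | 2.2 (0.90) | 0.44 (0.36) |
| 86% | 18.9 (1.00) | 9.5 (1.00) | 1.9 (0.86) |

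Cells show expected reports, with P(at least one) in brackets. They describe one observed dose, not the subject-level incidence that the trial will report, which also draws on the home doses.

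**5. Which outcome is touched?** The primary variables (7.4.1) are intraocular pressure, heart rate, blood pressure, pupil diameter and hyperemia, and H0/H1 (3.2) is built on these. Burning and stinging enter only through adverse-event incidence, a secondary variable (7.4.2).

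**The case against.** The strongest reply is that the observed doses are not where tolerability symptoms have to be caught. They serve the pre/post comparison of the primary variables. Adverse-event incidence counts subjects, so someone who burns at home counts, and 24 to 27 applications lie outside the two visits. Events are asked about at every visit with targeted questioning (7.4.5.9), all must be reported whatever their suspected cause (Table iii, 8.3), and unscheduled visits are available (7.7.5). This stands, and it limits the point: home symptoms are not lost, but they rest on recall over roughly two to five days between visits.

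Several stronger readings are tempting and are not supported.
- A reader might infer that symptoms *are* masked. The interval is unspecified. A site could do staining and tonometry first and then the vital signs, with their 20-minute rest (7.4.5.2), before dosing. The documents also give no duration of anaesthesia.
- A reader might infer that the reported incidence must be biased towards tolerable. That does not follow while home symptoms are elicited by questioning.
- A reader might infer that the diary has no symptom field. The protocol mentions none, but the diary itself is not among the documents.
- A reader might see a spoiled comparison with the 86% figure. Neither document plans one, and that product had different concentrations.

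**Conclusion.** The gap is real and modest. Anaesthetic before PRO-185 is built into both in-visit doses of the protocol schedule, no interval is stated, and the spacing rule does not reach this order. Burning and stinging can therefore be masked at the only doses with a scheduled 20-40 minute check in the protocol. For the remaining applications the documents describe questioning at later visits and no contemporaneous symptom record.

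The effect falls on the secondary adverse-event incidence that supports the tolerability objective. The H0/H1 test is untouched. The degree of masking is not known; the figures in the table show a range under assumed rates and shares. The count of 24 to 27 other applications depends on the day-1 number, and the count of two in-visit doses depends on how the baseline application is resolved. This is a low-cost improvement, not a fault that undermines the study.

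**What to change.** 1. Add to the existing Subject's Diary one line per application for burning or stinging on instillation: none, mild, moderate or severe. Tabulate it under expected adverse events as subject-level incidence. This gives prospective data on the home doses.
2. Record the times of the anaesthetic and PRO-185 drops at visits 1 and 2, and report in-clinic symptoms as following topical anaesthesia.
3. The sponsor should reconcile section 6.3 with 7.7.2 and 7.7.3 on the order and spacing of anaesthetic and study drop. It should also reconcile section 6.1.3, the protocol schedules and SAP Table 1 on whether a dose is given at the baseline visit. No interval or dosing rule is proposed here.

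Cost: one diary line per application, two recorded times per visit, and a sentence in the report. The downside is slightly more burden on subjects and more mild events recorded, so the tolerability figure may look less favourable.
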